3.5.2 Guidelines for Prolonged QTc

Guidelines for dose modification and stopping criteria due to QTc-prolongation are provided (see Table 8).

Table 8 Withholding and Stopping Criteria for QTc-Prolongation

QTc-Prolongation ^a	Action and Dose Modification

 • QTcB ≥ 501 msec, or • Uncorrected QT > 600 msec, or • QTcB > 530 msec for subjects with bundle branch block 	
 • Interrupt all study treatments until QTcB prolongation resolves to grade 1 or baseline • Test serum potassium, calcium, phosphorus and magnesium. If abnormal correct per routine clinical practice to within normal limits. • Review concomitant medication usage for a prolonged QTc. • Restart at current dose level^b • If event does not resolve or recurs after restarting, permanently discontinue study treatments.

Abbreviations: msec = milliseconds; QTcB = QT interval on electrocardiogram corrected using the Bazett's formula

A: Based on average QTc value of triplicate ECGs. For example, if an ECG demonstrates a prolonged QT interval, obtain two or more ECGs over a brief period, and then use the averaged QTc values of the three ECGs to determine if study treatments should be interrupted or discontinued.

B: If the QTc prolongation resolves to grade 1 or baseline, the subject may resume study treatment if the investigator and the subprotocol Study Chair agree that the subject will benefit from further treatment.

Rev. 12/16

3.5.3 Guidelines for Rash

Rash is a frequent AE observed in subjects receiving trametinib (see the Investigator's Brochures [4]) for more information).

Recommendations for supportive care and guidelines for dose modifications for rash are based on experience with other MEK inhibitors and EGFR inhibitors [26, 27] and are provided (see Table 9 and Table 10).

The institutional standards for the management of skin-related AEs can differ from these guidelines. In this case, best clinical judgment should be applied and a consultation with the subprotocol Study Chair may be required.

Table 9 Guidelines for Supportive Care of Rash

Type of Care	Action
Prevention/Prophylaxis ^a	
 • Avoid unnecessary exposure to sunlight • Apply broad-spectrum sunscreen (containing titanium dioxide or zinc oxide) with a skin protection factor (SPF) ≥ 15 at least twice daily. • Use thick, alcohol-free emollient cream (e.g., glycerine and cetomacrogol cream) on dry areas of the body at least twice daily. • Topical steroids and/or antibiotics should be applied at least twice daily starting on Day 1 of study treatment, to body areas such as face, chest, and upper back. Use mild-strength topical steroid (hydrocortisone 1% cream) and/or topical antibiotic (e.g., clindamycin) or oral antibiotics (e.g., doxycycline 100 mg BID, minocycline 100 mg BID)
Symptomatic Care ^b	
 • Pruritic lesions: cool compresses and oral antihistamine therapies • Fissuring lesions: Monsel's solution, silver nitrate, or zinc oxide cream • Desquamation: thick emollients and mild soap • Paronychia: antiseptic bath, local potent corticosteroids in addition to oral antibiotics; if no improvement, consult dermatologist or surgeon • Infected lesions: appropriate bacterial/fungal culture-driven systemic or topical antibiotics

Abbreviations: BID = twice daily; SPF = sun protection factor

- a. Rash prophylaxis is recommended for the first 6 weeks of study treatment
- b. Subjects who develop rash/skin toxicities should be seen by a qualified physician and should receive evaluation for symptomatic/supportive care management

Guidelines for management and dose reduction for rash considered to be related to study treatment are provided (see Table 10).

Table 10 Management and Dose Modification Guidelines for Rash

CTCAE Grade	Adverse Event Management	Action and Dose Modification
Grade 1	
 Initiate prophylactic and symptomatic treatment measures^a Use moderate strength topical steroid^b Reassess after 2 weeks 	
 Continue study treatment If rash does not recover to baseline within 2 weeks despite best supportive care, reduce trametinib by one dose level^c
Grade 2	
 Initiate prophylactic and symptomatic treatment measures Use moderate strength topical steroid^b Reassess after 2 weeks 	
 Reduce trametinib by one dose level 
 If rash recovers to ≤ grade 1 within 2 weeks, increase dose to previous dose level If no recovery to ≤ grade 1 within 2 weeks, interrupt study treatment until recovery to ≤ grade 1 Restart trametinib at reduced dose level^c
Grade ≥ 3	
 Use moderate strength topical steroids^b PLUS oral methyl-prednisolone dose pack Consult dermatologist 	
 Interrupt trametinib until rash recovers to grade ≤ 1 Restart^c trametinib reduced by one dose level^d If no recovery to grade ≤ 2 within 2 weeks, permanently discontinue trametinib

Abbreviations: CTCAE = Common Terminology Criteria for Adverse Events

- Rash prophylaxis is recommended for the first 6 weeks of study treatment
- Moderate-strength topical steroids: hydrocortisone 2.5% cream or fluticasone propionate 0.5% cream
- Approval of subprotocol Study Chair is required to restart study treatment after > 2 weeks of interruption.
- Escalation of study treatment to previous dose level may be considered if no rash is evident 4 weeks after restarting study treatment

Rev. 12/16

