3.4 Dose Modifications

NOTE: Patients who interrupt trametinib for > 2 weeks will be removed from this subprotocol, unless the interruption was for reduction in LVEF, visual changes or RPED with subsequent recovery as described in corresponding tables below.

All toxicity grades below are described using the NCI Common Terminology Criteria for Adverse Events (CTCAE) version 4.0.

All appropriate treatment areas should have access to a copy of the CTCAE version 4.0. A copy of the CTCAE version 4.0 can be downloaded from the CTEP website (<http://ctep.cancer.gov>).

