3.4.5 Pneumonitis Management Guidelines

Pneumonitis has been observed in subjects receiving trametinib. To reduce the risk of pneumonitis, subjects will be monitored closely for symptoms, evaluated with imaging and functional tests. Dose modification and supportive care guidelines for pneumonitis are described (see Table 6).

Table 6 Pneumonitis Guidelines for Trametinib

CTCAE Grade	Adverse Event Management	Action and Dose Modification
Grade 1	
 CT scan (high-resolution with lung windows) recommended Clinical evaluation and laboratory work-up for infection Monitoring of oxygenation via pulse-oximetry recommended Consultation with pulmonologist recommended 	
 Continue trametinib at current dose
Grade 2	
 CT scan (high-resolution with lung windows) recommended Clinical evaluation and laboratory work-up for infection Consult pulmonologist Pulmonary function tests -if < normal, repeat every 8 weeks until ≥ normal Bronchoscopy with biopsy and/or BAL recommended Symptomatic therapy including corticosteroids if clinically indicated 	
 Interrupt trametinib until recovery to grade ≤ 1 Restart treatment with trametinib reduced by one dose level Escalation to previous dose level after 4 weeks and consultation with the subprotocol Study Chair possible If no recovery to grade ≤ 1 within 2 weeks, permanently discontinue trametinib
Grade 3	
 Same as Grade 2 	
 Interrupt trametinib until recovery to grade ≤ 1 After consultation with the subprotocol Study Chair, treatment with trametinib may be restarted reduced by one dose level If no recovery to grade ≤ 1 within 2 weeks, permanently discontinue trametinib
Grade 4	
 Same as Grade 2 	
 Permanently discontinue trametinib

Abbreviations: BAL= bronchioalveolar lavage; CT = computed tomography; CTCAE = Common Terminology Criteria for Adverse Events

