3.5.5 Trametinib Dose Modification for Toxicities Not Specified in Subsequent Sections

Table 12 Trametinib Treatment Modification for Clinically Significant Toxicities Deemed Related to Trametinib

(This section is not for specific AEs such as hypertension, rash, ejection fraction changes, pneumonitis, diarrhea, liver chemistry, or visual changes. Refer to other sections for these specific AEs).

CTCAE v4 Grade	Management Guideline	Dose Modification
Grade 1	Monitor as clinically indicated. Provide supportive care according to institutional standards.	Continue trametinib at current dose level.
Grade 2 (tolerable)		
 Interrupt treatment until resolution to grade 1 or baseline. Upon resolution, restart treatment at current dose level.
Grade 2 (intolerable) and Grade 3		
 Interrupt treatment until resolution to grade 1 or baseline. Upon resolution to baseline or grade 1, restart with one level of dose reduction. If the Grade 3 toxicity recurs, interrupt trametinib; When toxicity resolves to Grade 1 or baseline, restart trametinib reduced by another dose level.
Grade 4		
If event resolves to grade 1 or baseline discuss potential continuation of trametinib with the subprotocol Study Chair; if continuation of treatment agreed then restart trametinib at dose reduced by one dose level.
 
If event does not resolve, permanently discontinue trametinib.

Trametinib should be discontinued if treatment delay is ≥ 14 days due to toxicities. If the investigator concludes that continued trametinib will benefit a patient, the subprotocol Study Chair may be consulted for the possibility of resuming trametinib, provided that toxicities have resolved to baseline or grade 1.

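### Section 3.4 removes a patient whose rash interruption passes 2 weeks, while Table 10 and its footnote c keep that patient on hold and allow restart with approval

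*Protocol*

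**What the plan says.** **Section 3.4, NOTE.** "Patients who interrupt trametinib for > 2 weeks will be removed from this subprotocol". The exceptions follow at once: "unless the interruption was for reduction in LVEF, visual changes or RPED with subsequent recovery as described in corresponding tables below". Rash is absent from that list, and the NOTE offers no route by which a longer interruption could be approved.

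**Section 3.5.3, Table 10, Grade ≥ 3 row.** The first instruction is "Interrupt trametinib until rash recovers to grade ≤ 1". Restart is then one dose level lower. The stop rule is "If no recovery to grade ≤ 2 within 2 weeks, permanently discontinue trametinib".

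**Table 10, Grade 2 row.** The dose is reduced first. If the rash has not come down to Grade 1 or lower within 2 weeks, drug is interrupted until it does, and is then restarted at the reduced level. The row sets no limit on the length of that interruption.

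**Table 10, footnote c.** It is attached to restart in both of these rows: "Approval of subprotocol Study Chair is required to restart study treatment after > 2 weeks of interruption".

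**The concern.** The NOTE and footnote c turn on the same condition, an interruption longer than 2 weeks, and attach different consequences to it. Under the NOTE the patient leaves the subprotocol. Under Table 10 the patient may still be on hold and may restart with approval. A site that reads Section 3.4 first will take the patient off. A site that works from the rash table will wait and ask the Study Chair. Both would be following the protocol.

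Time on treatment and the count of discontinuations for toxicity would then depend partly on which page was consulted. The arm has an accrual goal of 35, so a few such decisions would be visible in those summaries. The protocol's own adverse event list puts rash in its most frequent class (above 20%), so the table will be used. That class is not broken down by grade, however.

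**Working it through.** There is no figure to reproduce. The check sets the rules side by side and asks what each says about the same patient. The 2 weeks in the Grade ≥ 3 stop rule are taken to run from the interruption.

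**Step 1. Drug interrupted for Grade ≥ 3 rash, status at 2 weeks**

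| Rash grade at 2 weeks | Table 10 restart rule (Grade ≤ 1) | Table 10 stop rule (not yet Grade ≤ 2) | Outcome under Table 10 | Section 3.4 NOTE once the hold exceeds 2 weeks |
|---|---|---|---|---|
| 0–1 | met | not met | restart one level lower | not triggered if restart is within 2 weeks |
| 2 | not met | not met | hold continues; later restart with approval (footnote c) | removed |
| 3 or higher | not met | met | permanently discontinued | removed; same direction |

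Grade 2 is the only status at which the two rules part. The NOTE acts when the interruption exceeds 2 weeks, not on the day it reaches 2 weeks, so the conflict begins just after the Table 10 assessment.

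**Step 2. Drug interrupted under the Grade 2 row**

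The first 2 weeks in this row are spent on a reduced dose, so the NOTE's clock starts only at the later interruption. The row has no stop rule. If the rash needs more than 2 further weeks to reach Grade 1 or lower, the row and footnote c allow restart with approval, while the NOTE removes the patient. This conflict does not depend on the two different thresholds in the Grade ≥ 3 row.

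**Step 3. What work footnote c does**

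Footnote c concerns only restarts after more than 2 weeks off drug. If the NOTE governs rash, every patient it could apply to has already been removed, and the footnote has no effect. If the footnote governs, the NOTE's exception list is incomplete. The two cannot both stand as written.

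**Step 4. Whether another passage settles it**

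- Section 3.5.5 has a Study Chair route after a delay of 14 days or more, but it rules itself out here: "This section is not for specific AEs such as hypertension, rash, ejection fraction changes".
- Section 3.5.3 allows for institutional skin-care standards that differ from the guidelines: "In this case, best clinical judgment should be applied and a consultation with the subprotocol Study Chair may be required". That covers a difference between local practice and the protocol, not between two parts of the protocol.
- No passage says whether a specific table overrides the general NOTE.

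**The case against.** The strongest reply is that Table 10 is specific and complete on its own terms. Read alone, the Grade ≥ 3 row is an ordinary three-way rule: restart at Grade 1 or lower, stop if still above Grade 2 at 2 weeks, and otherwise keep holding, with later restart in the hands of one central approver. A specific table would usually be taken to displace a general note.

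Much of this stands. A reader might infer from the two thresholds that the row contradicts itself, or that a patient at Grade 2 has no instruction. The documents do not support that, because the first bullet of the row keeps such a patient on hold. Nor is the hold left wholly to the site: the row sets no maximum, but restart after more than 2 weeks needs Study Chair approval.

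A reader might also infer that the Grade 2 threshold can never decide anything. That follows only if the NOTE is assumed to override the table. Under Table 10 the threshold separates patients stopped at 2 weeks from those who may restart later.

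The pneumonitis rows in Table 6 use a single grade for restart and for stopping, but nothing requires different toxicities to share one pattern. That contrast is not evidence of an error.

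What does not stand is the appeal to precedence. The protocol states none, and the NOTE itself names the causes for which the tables below it apply instead. Leaving rash off that list weighs against reading in an unstated exception.

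**Conclusion.** The contradiction is real and lies between the Section 3.4 NOTE on one side and Table 10 with footnote c on the other. It affects any patient whose interruption for rash exceeds 2 weeks: under the Grade ≥ 3 row, those improved only to Grade 2 at 2 weeks; under the Grade 2 row, those slow to reach Grade 1 or lower once drug is interrupted. For each of them the protocol supports both removal and a continued hold with possible restart.

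The number affected cannot be derived. It would need the rate of rash by grade and the distribution of recovery times, and the protocol gives neither. A reader might try to turn the above-20% class into a count out of 35, but that class covers rash of every grade and says nothing about recovery at 2 weeks. An effect on a study endpoint cannot be shown from this document either. The defect is an ambiguous discontinuation rule that should be put right. It rests on the wording alone and on no assumed rate. Which of the two outcomes is clinically right is not judged here.

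**What to change.** Reconcile four pieces of text together: the Section 3.4 NOTE with its exception list, the Grade 2 row of Table 10, the Grade ≥ 3 row, and footnote c. After the change, a patient whose rash interruption passes 2 weeks, including one whose Grade ≥ 3 rash has improved only to Grade 2, should have exactly one stated outcome wherever the reader looks. The clinical team decides which.

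Editing only the thresholds in the Grade ≥ 3 row would not be enough, because the Grade 2 row and its footnote would still conflict with the NOTE.

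The cost is a short text amendment in Sections 3.4 and 3.5.3. It changes neither the accrual goal nor the assessment schedule.

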3.5.4 Guidelines for Diarrhea

Episodes of diarrhea have occurred in subjects receiving trametinib (see the Investigator Brochures [4] for more information). Other, frequent causes for diarrhea including concomitant medications (e.g., stool softeners, laxatives, antacids, etc.), infections by *C. difficile* or other pathogens, partial bowel obstruction, etc., should be clinically excluded.

Guidelines regarding management and dose reduction for diarrhea considered to be related to trametinib by the investigator are provided (see Table 11).

Table 11 Management and Dose Modification Guidelines for Diarrhea

CTCAE Grade	Adverse Event Management	Action and Dose Modification
Uncomplicated Diarrhea ^a Grade 1 or 2	
 • Diet: stop all lactose containing products; eat small meals, BRAT-diet (banana, rice, apples, toast) recommended • Hydration: 8-10 large glasses of clear liquids per day (e.g., Gatorade or broth) • Loperamide^c: initially 4 mg, followed by 2 mg every four hours or after every unformed stool; maximum 16 mg/day. Continue until diarrhea free for 12 hours • Diarrhea > 24h: loperamide 2 mg every two hours; maximum 16 mg/day. Consider adding oral antibiotics • Diarrhea > 48h: loperamide 2 mg every two hours; maximum 16 mg/day. Add budesonide or other second-line therapies (otretotide, or tincture of opium) and oral antibiotics 	
 • Continue trametinib • If diarrhea is grade 2 for > 48h, interrupt trametinib until diarrhea resolves to grade ≤1 • Restart trametinib at the same dose level • If treatment delay is > 14 days, discontinue trametinib.
Uncomplicated Diarrhea ^a Grade 3 or 4 Any Complicated Diarrhea ^b	
 • Clinical evaluation mandatory • Loperamide^c: initially 4 mg, followed by 2 mg every four hours or after every unformed stool; maximum 16 mg/day. Continue until diarrhea free for 12 hours • Oral antibiotics and second-line therapies if clinically indicated • Hydration: intravenous fluids if clinically indicated • Antibiotics (oral or intravenous) if clinically indicated • Intervention should be continued until the subject is diarrhea free for ≥ 24 hours • Intervention may require hospitalization for subjects at risk of life-threatening complications 	
 • Interrupt trametinib until diarrhea resolves to grade ≤1 • Restart with trametinib reduced by one dose level^d • If 3 dose reductions of study treatment are clinically indicated, permanently discontinue trametinib

Abbreviation: CTCAE = Common Terminology Criteria for Adverse Events

- **Uncomplicated diarrhea** defined by the absence of symptoms such as, cramping, nausea/vomiting ≥ grade 2, decreased performance status, pyrexia, sepsis, neutropenia grade ≥ 3, frank bleeding, and/or dehydration requiring intravenous fluid substitution
- **Complicated diarrhea** defined by the presence of symptoms such as, cramping, nausea/vomiting ≥ grade 2, decreased performance status, pyrexia, sepsis, neutropenia grade ≥ 3, frank bleeding, and/or dehydration requiring intravenous fluid substitution
- Loperamide should be made available prior to start of study treatment so loperamide administration can begin at the first signs of diarrhea
- Escalation of trametinib to previous dose level is allowed after consultation with the Subprotocol Study Chair and in the absence of another episode of complicated or severe diarrhea in the 4 weeks subsequent to dose reduction.

3.5.5 Trametinib Dose Modification for Toxicities Not Specified in Subsequent Sections

Table 12 Trametinib Treatment Modification for Clinically Significant Toxicities Deemed Related to Trametinib

(This section is not for specific AEs such as hypertension, rash, ejection fraction changes, pneumonitis, diarrhea, liver chemistry, or visual changes. Refer to other sections for these specific AEs).

CTCAE v4 Grade	Management Guideline	Dose Modification
Grade 1	Monitor as clinically indicated. Provide supportive care according to institutional standards.	Continue trametinib at current dose level.
Grade 2 (tolerable)		
 Interrupt treatment until resolution to grade 1 or baseline. Upon resolution, restart treatment at current dose level.
Grade 2 (intolerable) and Grade 3		
 Interrupt treatment until resolution to grade 1 or baseline. Upon resolution to baseline or grade 1, restart with one level of dose reduction. If the Grade 3 toxicity recurs, interrupt trametinib; When toxicity resolves to Grade 1 or baseline, restart trametinib reduced by another dose level.
Grade 4		
If event resolves to grade 1 or baseline discuss potential continuation of trametinib with the subprotocol Study Chair; if continuation of treatment agreed then restart trametinib at dose reduced by one dose level.
 
If event does not resolve, permanently discontinue trametinib.

Trametinib should be discontinued if treatment delay is ≥ 14 days due to toxicities. If the investigator concludes that continued trametinib will benefit a patient, the subprotocol Study Chair may be consulted for the possibility of resuming trametinib, provided that toxicities have resolved to baseline or grade 1.

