	Abdominal pain		Abdominal pain (Gr 2)
		Colitis	
		Colonic perforation	
	Constipation		Constipation (Gr 2)

Adverse Events with Possible Relationship to Trametinib (GSK1120212B) (CTCAE 5.0 Term) [n= 1111]			Specific Protocol Exceptions to Expedited Reporting (SPEER)
Likely (>20%)	Less Likely (<=20%)	Rare but Serious (<3%)	
Diarrhea			Diarrhea (Gr 3)
	Dry mouth		Dry mouth (Gr 2)
	Dyspepsia		Dyspepsia (Gr 2)
	Mucositis oral		Mucositis oral (Gr 3)
Nausea			Nausea (Gr 3)
	Vomiting		Vomiting (Gr 3)
GENERAL DISORDERS AND ADMINISTRATION SITE CONDITIONS			
	Chills		Chills (Gr 2)
	Edema face		
Fatigue			Fatigue (Gr 3)
	Fever		Fever (Gr 2)
Generalized edema			Generalized edema³ (Gr 2)
IMMUNE SYSTEM DISORDERS			
	Allergic reaction ⁴		
INFECTIONS AND INFESTATIONS			
	Folliculitis		Folliculitis (Gr 2)
	Lung infection		
	Paronychia		Paronychia (Gr 2)
	Skin infection		Skin infection (Gr 2)
INVESTIGATIONS			
	Alanine aminotransferase increased		Alanine aminotransferase increased (Gr 3)
	Alkaline phosphatase increased		Alkaline phosphatase increased (Gr 2)
	Aspartate aminotransferase increased		Aspartate aminotransferase increased (Gr 3)
	CPK increased		
	Ejection fraction decreased		
METABOLISM AND NUTRITION DISORDERS			
	Anorexia		Anorexia (Gr 3)
	Dehydration		Dehydration (Gr 3)
	Hypoalbuminemia		
	Hypomagnesemia		Hypomagnesemia (Gr 2)
	Hyponatremia		Hyponatremia (Gr 3)
MUSCULOSKELETAL AND CONNECTIVE TISSUE DISORDERS			
	Arthralgia		
	Back pain		Back pain (Gr 2)
	Pain in extremity		Pain in extremity (Gr 2)
		Rhabdomyolysis	
NERVOUS SYSTEM DISORDERS			
	Dizziness		Dizziness (Gr 2)
	Headache		Headache (Gr 2)

Adverse Events with Possible Relationship to Trametinib (GSK1120212B) (CTCAE 5.0 Term) [n= 1111]			Specific Protocol Exceptions to Expedited Reporting (SPEER)
Likely (>20%)	Less Likely (<=20%)	Rare but Serious (<3%)	
RESPIRATORY, THORACIC AND MEDIASTINAL DISORDERS			
	Cough		Cough (Gr 2)
	Dyspnea		Dyspnea (Gr 3)
		Pneumonitis	
SKIN AND SUBCUTANEOUS TISSUE DISORDERS			
	Alopecia		Alopecia (Gr 2)
	Dry skin		Dry skin (Gr 2)
	Nail changes		
		Palmar-plantar erythrodysesthesia syndrome	
	Pruritus		Pruritus (Gr 2)
		Skin and subcutaneous tissue disorders - Other (drug reaction with eosinophilia and systemic symptoms [DRESS])	
Skin and subcutaneous tissue disorders - Other (rash) ⁵			Skin and subcutaneous tissue disorders - Other (rash)⁵ (Gr 3)
		Stevens-Johnson syndrome ⁶	
VASCULAR DISORDERS			
	Hypertension		Hypertension (Gr 3)

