3.5.1 Trametinib Dose Modification for Liver Chemistry Changes

Table 7: Trametinib Dose Modification for Liver Function Test Abnormalities

Event	Treatment modifications and assessment/monitoring

ALT \geq 3x ULN but < 5x ULN and TB < 2x ULN, without symptoms considered related to liver injury or hypersensitivity and who can be monitored weekly for 4 weeks
	
 • May continue study drug. • Report as SAE if CTEP-AERS reporting criteria is met. • If liver chemistry stopping criteria are met any time, proceed as described below. 
MONITORING: Repeat LFT (ALT, AST, ALK, bilirubin) until they return to normal/baseline or stabilise (LFT may be every 2 weeks after 4 weeks if ALT < 3x ULN and TB < 2 ULN). If baseline ALT and Tbili already meet these criteria, then monitoring is required only if ALT or TB rises after initiation of study therapy.

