
Criteria for discontinuing study drug: When any of the liver stopping criteria below is met, discontinue trametinib
 
 1. ALT \geq3xULN and bilirubin \geq 2x ULN or >35% direct bilirubin ^{1,2} 2. ALT \geq 3xULN and INR >1.5, if INR measured² (INR threshold does not apply if subject is on anticoagulant) 3. ALT \geq 5x ULN 4. ALT \geq 3x ULN persists for \geq 4 weeks. However, if ALT was elevated 3-5x at baseline due to liver mets, then this criteria should not be used for treatment discontinuation UNLESS the ALT improves to < 3x ULN and then subsequently rises. 5. ALT \geq 3x ULN and cannot be monitored weekly for 4 weeks. However, if ALT was elevated 3-5x at baseline due to liver mets, then this criteria should not be used for treatment discontinuation UNLESS the ALT improves to < 3x ULN and then subsequently rises. 6. ALT \geq 3x ULN associated with symptoms³ (new or worsening) believed to be related to liver injury or hypersensitivity 	
 • Immediately discontinue study treatment. • Do not restart/rechallenge unless approved by the subprotocol Study Chair. [• Report as SAE if: 1) CTEP-AERS reporting criteria are met, or 2) patients meet criteria 1-2. • Perform liver event ASSESSMENT AND WORKUP (see below). • Monitor the subject until liver chemistries resolve, stabilize, or return to baseline (see MONITORING below). • If applicable, provide details on required follow up assessments (e.g., follow up for overall survival or disease recurrence or progression). [Do not include for single-dose studies] 
MONITORING: In patients stopping for criteria 1-2 (with abnormal TB and INR, indicating potentially more significant liver toxicities):
 
 • Repeat liver chemistries (ALT, AST, ALK, bilirubin) and perform liver event follow-up assessments within 24 hours. • Monitor subjects twice weekly until LFT return to normal/baseline or stabilize. • A specialist or hepatology consultation is recommended. 
In patients stopping for criteria 2-6:
 
 • Repeat LFT and perform liver event follow up assessments within 24-72 hrs • Monitor subjects weekly until LFTs return to normal/baseline or stabilize. 
ASSESSMENT and WORKUP:
 
 • Viral hepatitis serology.⁴ • Serum CPK and LDH. • Fractionate bilirubin, if total bilirubin \geq 2x ULN. • CBC with differential to assess eosinophilia. • Record clinical symptoms of liver injury, or hypersensitivity on AE CRF. • Record concomitant medications (including acetaminophen, herbal

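### Table 12 excludes liver chemistry and every entry of Table 7 needs ALT at or above 3x ULN, so a severe AST or alkaline phosphatase rise with lower ALT has no specific graded dose rule

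*Protocol*

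**What the plan says.** Section 3.5.5 is headed "Trametinib Dose Modification for Toxicities Not Specified in Subsequent Sections". Its Table 12 gives an action by CTCAE grade for clinically significant toxicities judged related to trametinib. A scope note beneath the table title narrows it: "This section is not for specific AEs such as hypertension, rash, ejection fraction changes, pneumonitis, diarrhea, liver chemistry, or visual changes". The note then adds: "Refer to other sections for these specific AEs".

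For liver events the only other section is 3.5.1, headed "Trametinib Dose Modification for Liver Chemistry Changes", which contains Table 7. Table 7 has two event rows:

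- The continue-and-monitor row opens with "ALT \geq 3x ULN but < 5x ULN and TB < 2x ULN" and is limited to patients "without symptoms considered related to liver injury or hypersensitivity and who can be monitored weekly for 4 weeks".
- The stopping row says "When any of the liver stopping criteria below is met, discontinue trametinib" and lists six criteria. Each starts from ALT at or above 3x ULN, or at or above 5x ULN.

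The monitoring text in Table 7 names four tests as liver chemistries: ALT, AST, alkaline phosphatase and bilirubin. Section 4.1, footnote B, includes the same four in the serum chemistry panel taken at the start of each cycle.

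**The concern.** The scope note removes liver chemistry from the general table as a whole category, without reference to ALT. The table it points to accepts only part of that category. A patient whose AST or alkaline phosphatase is severely raised while ALT stays below 3x ULN is sent from Table 12 to Table 7 and finds no row there.

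The stake is patient safety, together with consistent handling across sites. Two investigators with the same laboratory result could reasonably act differently: one could apply Table 12 on the strength of its heading, and the other could find no rule on the strength of its scope note. The events are foreseeable. The CAEPR in section 3.3 lists AST and alkaline phosphatase increases as possibly related to trametinib, and both tests are measured every cycle.

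**Working it through.** The plan states no figure to reproduce, and no sample size, power or error rate is involved. The check is one of logical coverage.

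**Step 1: can any Table 7 entry be met with ALT below 3x ULN?**

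| Table 7 entry | ALT condition | Further condition | Can be met with ALT < 3x ULN? |
|---|---|---|---|
| Continue row | ≥ 3x and < 5x ULN | total bilirubin < 2x ULN, no related symptoms, weekly monitoring possible | No |
| Stop 1 | ≥ 3x ULN | bilirubin ≥ 2x ULN or > 35% direct | No |
| Stop 2 | ≥ 3x ULN | INR > 1.5, if measured | No |
| Stop 3 | ≥ 5x ULN | none | No |
| Stop 4 | ≥ 3x ULN | persists ≥ 4 weeks | No |
| Stop 5 | ≥ 3x ULN | weekly monitoring not possible | No |
| Stop 6 | ≥ 3x ULN | related symptoms | No |

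Entries: 1 + 6 = 7. Entries open to a patient with ALT below 3x ULN: 0 of 7. AST and alkaline phosphatase appear in Table 7 only as tests to repeat, never as a trigger. Bilirubin triggers a stop only jointly with ALT.

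The direct-bilirubin limb of criterion 1 is loosely worded and could be read as standing alone. Footnote 2 to Table 7 ties it to bilirubin ≥ 2x ULN and to ALT ≥ 3x ULN, so the count is unchanged. Even the loose reading would not reach AST or alkaline phosphatase.

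**Step 2: does Table 12 catch the remainder?** By its scope note, no: liver chemistry is named and excluded without qualification. The heading points the other way, since an event that no table specifies is on its face an unspecified toxicity. The heading is itself inexact. It speaks of later sections, but the specific tables stand in 3.4.3 to 3.5.4, before it, and only supportive care and the durations of treatment and follow-up (3.6 to 3.8) come after it in section 3.

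**Step 3: does anything else catch it?** Section 3.1 continues treatment until intolerable toxicity or progression. Section 3.7 ends it for unacceptable toxicity, or where the protocol's constraints harm the patient. Both apply to a liver event. Neither gives a grade or laboratory threshold, a hold, a dose step or a restart condition. The note opening 3.4 (removal after an interruption of more than 2 weeks, with exceptions) and 3.4.2 (re-escalation, and the floor of 1 mg) operate only after an interruption or reduction has been made. The subprotocol does not refer to the MATCH Master Protocol for liver dose modification.

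**Step 4: a comparison within the document.** A CPK increase is also listed in the CAEPR, has no table of its own and is not named in the scope note. A related Grade 3 CPK rise therefore receives Table 12's hold, reduce and restart sequence. A related Grade 3 AST rise with ALT below 3x ULN receives no graded rule. Nothing in the protocol explains the difference.

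**The case against.** The best case on the other side is that the scope note only prevents two tables from governing one event. Its list is introduced as illustrative: QTc prolongation has its own Table 8 and is not named. On that reading, a liver event that Table 7 does not specify stays unspecified and falls to Table 12, as the heading suggests. This has some force, and it means the text is ambiguous rather than certainly empty. It does not remove the point, because liver chemistry is excluded by name and the reader is told to look elsewhere. Two statements that lead to different handling of the same result need reconciling whichever was meant.

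A second argument is that keying liver stopping criteria to ALT is a legitimate design choice. That stands, and this point does not dispute it. The defect lies in closing the general table to the events that choice leaves out.

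A third argument concerns bilirubin. Section 3.3 lists a bilirubin increase among events with insufficient evidence of causation, and Table 12 covers only toxicities deemed related. An isolated bilirubin rise might therefore not enter Table 12 even without the exclusion. This stands: bilirubin belongs in the point only where the investigator judges the rise related.

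A reader might also infer that the protocol permits full dosing to continue through any isolated Grade 3-4 liver abnormality. It does not go that far, because the general stops in 3.1 and 3.7 remain available to the investigator. What is missing is a specific graded rule.

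**Conclusion.** The point holds in a limited form. Read literally, a trametinib-related Grade 3-4 rise in AST or alkaline phosphatase (or in bilirubin, if judged related) with ALT below 3x ULN meets 0 of 7 entries in Table 7 and is excluded by name from Table 12. No specific graded hold, reduction, restart or stopping rule in this subprotocol then applies. The general toxicity stops cushion the gap, so it is a correctable safety-rule defect rather than an absence of all protection.

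The conclusion assumes that the scope note means what it says, and that liver chemistry has the meaning Table 7 gives it. The Master Protocol is not at hand.

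Two further inferences are tempting and not supported:

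- **Frequency.** The CAEPR places AST and alkaline phosphatase increases in its band of up to 20%. That is a ceiling with no breakdown by severity and no reference to ALT, so it does not show how many of the planned 35 patients would have a severe rise with ALT below 3x ULN. The protocol gives no figure for these events.
- **Under-reporting.** The subprotocol's expedited liver triggers (3.2.1) also need ALT ≥ 3x ULN, but they are additional to Master Protocol rules that are not shown. The reporting exception through Grade 3 covers ALT as well as AST, so it is unrelated to the gap between the two dose tables.

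**What to change.** Reconcile three texts: the 3.5.5 heading, the Table 12 scope note and the entry conditions of Table 7. After the change, exactly one table should govern each liver chemistry that Table 7 names and 4.1 footnote B measures, and the text should say which table applies to a liver event that meets no Table 7 entry. The heading's reference to later sections should be corrected in the same edit, since the specific tables precede it.

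Which clinical action then applies is for the medical team to decide and is not proposed here. The cost is about one sentence in the scope note and a corrected heading. No tests, visits or data items are added, because the analytes are already measured every cycle.
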